**A Comparison of Lidocaine, Esmolol, and Placebo Without Use of a
Tourniquet for Relieving Pain from Intravenous Administration of Propofol**

IRB00063576NCT

NCT 04356352

IRB Approval Date: 08JUN2022

Study Title: A Comparison of Lidocaine, Esmolol, and Placebo Without Use of a Tourniquet for Relieving Pain from Intravenous Administration of Propofol

Principal Investigator, Co-investigator(s): [name]; [name]; [name]; [name]; [name]; [name]; [name]; [name], DNP, CRNA; [name], CRNA; [name]; [name]; [name]; [name]; [name]; [name]

Sponsor or funding source: Department of Anesthesiology

Background

It has long been known that propofol causes pain on intravenous injection (1). This pain is multifactorial in origin, stemming from direct mucosal irritation as well as stimulation of nociceptive sensory nerve fibers in the venous adventitia (2). Lidocaine has frequently been administered either in advance or concomitantly with propofol to attenuate this response. Studies have noted varying degrees of success with this technique but have clearly demonstrated an improvement in propofol injection pain when lidocaine is administered in combination with venous occlusion by a tourniquet (3, 4, 5, 6, 7).

Adrenergic signaling pathways participate in the neurotransmission and modulation of pain. α_2 agonists have been shown to work synergistically with opioids to exert anti-nociceptive effects (8), and α_1 antagonists possess similar properties (9). Esmolol has been shown to decrease perioperative anesthetic and narcotic requirements (10, 11), and one study showed that perioperative esmolol administration decreased postoperative opioid requirements for up to three days after surgery (12). Another study demonstrated that an intraoperative esmolol infusion decreased emergence times, postoperative narcotic requirements, and the time to discharge after ambulatory surgery (13). Esmolol has also been found useful for decreasing pain upon injection of a venous irritant: it decreases the pain associated with rocuronium injection (14) and may be even more effective than lidocaine at attenuating propofol injection pain when used in combination with a tourniquet (15). Importantly, it has proven to be effective at blunting the cardiovascular response to a noxious stimulus without causing clinically significant bradycardia and hypotension (16).

Despite the results of the above cited studies, most clinicians seldom use a tourniquet when giving lidocaine to attenuate propofol injection pain. In addition, esmolol's utility in preventing this pain has not been studied in the absence of a tourniquet. The goal of the present study is to determine whether lidocaine or esmolol is effective at preventing propofol injection pain when a tourniquet is not used.

In clinical practice, we commonly administer IV lidocaine from premixed syringes containing 100 mg of the drug dissolved in 5 ml. Most providers administer 1 mg/kg body weight, and few if any will open a second syringe when patients weigh more than 100 kg. Since the goal of this trial is to observe the clinical efficacy of this drug when administered the way it is usually done

by practicing clinicians, we decided to administer 1 mg/kg lidocaine to a maximum of 100 mg. In order to maintain blinding and consistency in this trial, we decided esmolol should be administered to a maximum of 50 mg since it will be mixed to half the concentration of the lidocaine -- this ensures that an equal volume of study drug will be administered, thus helping us maintain double blinding.

The study will include three arms: lidocaine, esmolol, and placebo. Eligible patients will be 18-60 years old, ASA physical status 1-3, and scheduled for an elective surgical procedure. Patients will be randomized to receive lidocaine, esmolol, or placebo. Both the patients and the administering/observing providers will be blinded to the study drug or placebo being administered.

Objectives

Our primary hypothesis is that esmolol and lidocaine, when given without the use of a tourniquet, provide relief of propofol injection pain that is superior to placebo when assessed using our propofol pain scoring tool.

Setting

This study is taking place at Wake Forest Baptist Medical Center in the perioperative setting. Subjects will already be planning on having an elective surgical procedure and be anticipating having a general anesthetic receiving propofol as part of that procedure.

Subjects selection criteria

Inclusion criteria

- 18-60 years of age
- ASA 1-3
- Elective surgical procedure

Exclusion criteria

- BMI \geq 45
- Pregnancy
- Requirement for RSI or awake intubation
- Suspected or known difficult airway
- Any use of opioids in the last week
- Significant cardiopulmonary or hepatic dysfunction
- Hypersensitivity to study medications

Study Procedures, Interactions and Interventions

- Obtain informed consent and randomize patient into one of three groups (lidocaine, esmolol, placebo)
- Dose medications based on actual body weight
- Start 20 gauge IV in either extremity and hang lactated ringers (LR)
- Administer no sedative or analgesic (i.e., no Versed or fentanyl) prior to induction
- Place standard monitors and preoxygenate patient

- Administer study medication as a bolus
 - 1 mg/kg lidocaine to a max of 100 mg, 0.5 mg/kg esmolol to a max of 50 mg, or placebo
 - Lidocaine will be 20 mg/ml and esmolol will be 10 mg/ml
 - These concentrations allow us to simply administer 0.05 ml solution per kg regardless of which group the patient has been randomized into – 100 kg patient would receive 5 ml solution that would contain 100 mg lidocaine (= 1 mg/kg), 50 mg esmolol (= 0.5 mg/kg), or saline
 - Allow patient's IV to run freely
- 20-30 seconds after administration of study medication, bolus 0.5 mg/kg propofol to a max of 50 mg
- Record patient's pain over the next thirty seconds
 - Use the pain scale previously published by McCririck and Hunter (Anaesthesia 1990;45(6):443-4).
 - 0 = no pain
 - 1 = mild pain
 - Pain reported in response to questioning AND NOT accompanied by a physical sign (grimacing, withdrawal, tears, etc.)
 - 2 = moderate pain
 - Pain reported in response to questioning AND accompanied by a physical sign
 - Pain reported spontaneously AND NOT accompanied by a physical sign
 - 3 = severe pain
 - Pain eliciting a strong vocal response
 - Pain reported spontaneously AND accompanied by a physical sign
- Proceed with induction at the discretion of the attending anesthesiologist
 - If patient requires a NDMB, use vecuronium instead of rocuronium (due to venous irritation caused by rocuronium)
- Record vital signs every minute after induction for ten minutes
 - Also record administration of any medications given to treat hemodynamic derangements during this time frame (phenylephrine, ephedrine, propofol, etc.)
 - Do not administer esmolol for tachycardia during this time frame unless the patient shows evidence of myocardial ischemia or other significant derangements

Sample Size

150 patients (50 in each arm) is anticipated to be needed in this study.

Outcome Measure

Our primary outcome measure will be the proportion of patients with pain using a pain scoring system previously used by studies looking at various remedies to decrease propofol injection pain (15, 17). In this scoring system, patients are observed and their responses and behaviors are rated according a specific rubric (Table 1) (17). This assessment will be performed by a blinded

member of the study team following administration of a sub-induction dose of propofol, 0.5 mg/kg up to 50 mg, just prior to full induction.

Our secondary outcome measure will be heart rate, blood pressure, and SpO₂ every minute following induction. We will record vital signs each minute for the first 10 minutes following induction.

Analytical Plan

In preparation for this study, we obtained pilot data using five patients in each of the three proposed study arms. As shown in Table 2, lidocaine and esmolol both decreased the incidence of propofol injection pain in relation to placebo. Given that 40% (95% CI 0-83%) and 60% (95% CI 17-100%) patients given lidocaine and esmolol respectively reported little to no pain defined as a pain score of 0 on our propofol pain injection while 0% of patients who received placebo reported no pain, we used a sample size calculator for proportions with a 25% difference considered clinically significant, 90% power, and a 95% confidence level to determine a sample size of 32. In order improve our certainty we will increase this to 50 patients per group.

We will perform descriptive statistics on all demographic data. We will perform an individual comparison of all three groups using Pearson's chi-square test with Bonferroni correction for multiple comparisons. Other inferential statistics will be performed as necessary.

Human Subjects Protection

Subject Recruitment Methods

Subjects will be identified through the daily review of the preanesthesia assessment clinic as well as the daily surgical schedule for those meeting inclusion criteria. They will then be approached by a member of the research staff regarding their participation.

Informed Consent

Written informed consent will be obtained by a member of the research staff discussing this study in depth with them. Adequate time will be given for the subject to consider their participation. The risk of harm or discomfort that may occur as a result of taking part in this research study is not expected to be more than in daily life or from routine physical or psychological examinations or tests. The rights and welfare of study will be protected through the use of measures to maintain the confidentiality of study information. Study results will be presented or published in lieu of providing individual subjects additional information regarding the study.

Confidentiality and Privacy

Confidentiality will be protected by collecting only information needed to assess study outcomes, minimizing to the fullest extent possible the collection of any information that could directly identify subjects, and maintaining all study information in a secure manner. To help ensure subject privacy and confidentiality, only a unique study identifier will appear on the data

collection form. Any collected patient identifying information corresponding to the unique study identifier will be maintained on a linkage file, stored separately from the data. The linkage file will be kept secure, with access limited to designated study personnel. Following data collection subject identifying information will be destroyed per institutional guidelines (investigator initiated research data maintained for 6 years) consistent with data validation and study design, producing an anonymous analytical data set. Data access will be limited to study staff. Data and records will be kept locked and secured, with any computer data password protected. No reference to any individual participant will appear in reports, presentations, or publications that may arise from the study.

Data and Safety Monitoring

The principal investigator will be responsible for the overall monitoring of the data and safety of study participants. The principal investigator will be assisted by other members of the study staff. [name] will serve as a project mentor and will be involved in planning the study, navigating the IRB process, collecting and analyzing data, and preparing and submitting the manuscript.

Reporting of Unanticipated Problems, Adverse Events or Deviations

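### No pre-drug reading is called for in the only named secondary outcome (heart rate, blood pressure, SpO2); one baseline set, used as a covariate, could sharpen an already unbiased comparison at little cost

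*Combined protocol and SAP*

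**What the plan says.** The Outcome Measure section opens its secondary outcome with "Our secondary outcome measure will be heart rate, blood pressure" and adds SpO2. It fixes the schedule as "We will record vital signs each minute for the first 10 minutes following induction". The section Study Procedures, Interactions and Interventions gives the same window: "Record vital signs every minute after induction for ten minutes".

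Earlier in that procedures list, before the study-drug bolus, comes the step "Place standard monitors and preoxygenate patient". It carries no instruction to write down a reading.

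The Analytical Plan names a chi-square test with Bonferroni correction for comparing the three groups, which suits the pain proportion. For anything else it has only a general provision for further inferential statistics as needed. It mentions no model, summary measure or baseline adjustment for the vital signs.

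Allocation is by chance ("Patients will be randomized to receive lidocaine, esmolol, or placebo"), and the Sample Size section gives 50 patients per arm.

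**The concern.** Patients arrive with different resting heart rates and blood pressures, and that spread carries over in part into their readings after induction. If nothing is recorded before the study drug, all of it stays in the error term of the between-arm comparison. A pre-drug reading used as a covariate removes the part it predicts.

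What is at stake is how small a hemodynamic difference 50 patients per arm can show. A wide interval around a vital-sign difference says little either way, and one arm receives a beta-blocker. The monitors are already attached at the right moment, so the information is available and only needs to be written down.

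**Working it through.** **The plan's own figure.** The documents give no precision or power figure for the vital signs. Their one calculation, 32 per group, is for pain. It reproduces with 0% versus 25%, unpooled variance, two-sided alpha 0.05 and 90% power: (1.960 + 1.282)² × (0.25 × 0.75) / 0.25² = 31.5, rounded up to 32. It has no bearing on the vital signs and is not in question here.

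**Inputs for the illustration**
- n = 50 per arm (Sample Size).
- Three pairwise comparisons with Bonferroni, two-sided alpha 0.05/3 = 0.0167. The Analytical Plan states Bonferroni for the chi-square comparison; carrying it over to the vital signs is this review's choice.
- Power of 90% (the plan's level for pain) and 80% (for comparison).
- Summary: each patient's mean over the ten minutes. This is this review's choice; the plan defines only minute-by-minute readings.
- r, the correlation of the pre-drug reading with that mean. The documents do not give it, so 0.3, 0.5 and 0.7 are assumed.
- A baseline for every patient (assumed).

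**Formulas**, in units of the between-patient SD of the 10-minute mean:
- Without a baseline: d = (z for alpha + z for power) × √(2/50), where √(2/50) = 0.2.
- With the baseline as covariate: d × √(1 − r²).

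**Results**
- Without a baseline, 80% power: (2.394 + 0.842) × 0.2 = 0.647.
- Without a baseline, 90% power: (2.394 + 1.282) × 0.2 = 0.735.

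| Assumed r | √(1 − r²) | 80% power | 90% power | Reduction |
|---|---|---|---|---|
| no baseline | 1 | 0.65 SD | 0.74 SD | – |
| 0.3 | 0.954 | 0.62 SD | 0.70 SD | 5% |
| 0.5 | 0.866 | 0.56 SD | 0.64 SD | 13% |
| 0.7 | 0.714 | 0.46 SD | 0.52 SD | 29% |

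The percentage reduction depends only on r, so it is the same at any alpha or power. In terms of information, 50/(1 − r²) gives the equivalent of about 55, 67 or 98 patients per arm.

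**Bias check.** In 20,000 simulated two-arm comparisons (50 per arm, r = 0.6, true difference 0.5 SD), the mean estimate was 0.499 without the baseline and 0.500 with it. The spread of the estimates fell from 0.200 to 0.162. Leaving the baseline out costs precision and adds no bias.

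**Covariate or change score.** With equal SDs before and after, the standard error of a change-score comparison is 0.2 × √(2(1 − r)): 0.237 at r = 0.3, 0.200 at r = 0.5 and 0.155 at r = 0.7. Post-induction values alone give 0.200, and the covariate analysis gives 0.191, 0.173 and 0.143. A change score is therefore worse than no baseline when r is below 0.5. The covariate analysis is better than either at all three values.

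**Incomplete baselines.** The documents do not give enrolment status. If, for example, half of each arm had a baseline, relative information would be 0.5/(1 − r²) + 0.5, or 1.05, 1.17 and 1.48. The reductions would fall to about 2%, 7% and 18%.

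**The case against.** The strongest reply is that this is a refinement and not an error. The Objectives section states a hypothesis about pain only ("Our primary hypothesis is that esmolol and lidocaine, when given without the use of a tourniquet, provide relief of propofol injection pain"). The plan sets no precision target for vital signs, so there is none that it misses. The size of the gain rests on a correlation that the documents do not give. Induction is at the attending anesthesiologist's discretion, and drugs for hemodynamic changes are allowed in the same ten minutes; both could weaken the link between pre-drug and later values. SpO2 is capped at 100% and is read after preoxygenation, so it may gain least. Averaging over ten minutes could also dilute a difference confined to the early minutes. All of this stands, and it keeps the point minor. It does not remove the point, because the reading costs almost nothing.

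Three stronger readings are tempting, and the documents support none of them.

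- **That the comparison is biased without a baseline.** Randomization makes the arms comparable in expectation before the study drug, and the simulation agrees.
- **That no baseline will exist.** The protocol does not call for one, but neither does it say that none will be taken, and a reading may sit in the routine anesthetic record. The statement under Confidentiality and Privacy, "Confidentiality will be protected by collecting only information needed to assess study outcomes", does not settle this: it is a privacy safeguard, and a baseline could count as needed information.
- **That drugs given for hemodynamic changes will hide an esmolol effect.** Their use is recorded ("Also record administration of any medications given to treat hemodynamic derangements during this time frame"), but the documents give no rates by arm, so no distortion can be shown.

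**Conclusion.** The point holds as a minor improvement to the secondary outcome. No pre-drug vital signs are called for, and no specific analysis of these signs is given. The comparison of arms after induction remains unbiased with respect to the missing baseline, and the primary pain analysis and its sample size are untouched.

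The 5%, 13% and 29% reductions rest on the assumed correlations, on the 10-minute mean as summary and on a baseline for every patient. Each is therefore an upper value for its correlation, and the true gain may be small.

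**What to change.** 1. Add one line to the procedures and the data form: after the monitors are placed and immediately before the study drug, record heart rate, blood pressure and SpO2. The reading must come before the study drug. A later one could already reflect the drug, and adjusting for it could remove part of the effect.
2. State the analysis in the Analytical Plan. For each sign, fit a repeated-measures model with arm, minute, arm by minute and the pre-drug reading as covariate, not a simple change score. Take the arm difference averaged over the ten minutes as the main contrast, and show the minute-by-minute differences beside it so that an early effect is not lost. Apply Bonferroni over the three pairs.
3. Keep patients without a baseline in the analysis, for example by modelling the baseline and the ten readings jointly with one baseline mean common to the arms.

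As a side note, report use of drugs for hemodynamic changes by arm next to the vital signs.

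The cost is one data-form line read from monitors already attached, a few sentences of plan and slightly more analysis. No procedure, staff or clinical rule changes. The limitation is that a newly added reading helps only patients not yet treated.

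### Does sizing the trial without the Bonferroni correction leave the planned tests underpowered at 50 per arm?

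*Combined protocol and SAP*

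**What the plan says.** The Analytical Plan starts from a pilot of five patients per arm. Pain-free rates were "40% (95% CI 0-83%) and 60% (95% CI 17-100%) patients given lidocaine and esmolol respectively", and "0% of patients who received placebo reported no pain"; Table 2 in the Appendix gives the same counts as incidence of pain. The sizing sentence reads "we used a sample size calculator for proportions with a 25% difference considered clinically significant, 90% power, and a 95% confidence level", and the calculator was used "to determine a sample size of 32". The investigators then add: "In order improve our certainty we will increase this to 50 patients per group". The Sample Size section agrees: "150 patients (50 in each arm) is anticipated to be needed in this study".

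The next paragraph of the Analytical Plan sets out the analysis as "an individual comparison of all three groups" by Pearson's "chi-square test with Bonferroni correction for multiple comparisons". It gives no divisor, and no power at 50 per arm or at the corrected level. The Objectives section limits the primary hypothesis to each active drug against placebo.

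**The concern.** The sizing sentence and the analysis sentence use different significance levels. The sample size comes from an uncorrected 5% test; the analysis divides the 5% over several tests. The increase from 32 to 50 is not presented as an allowance for multiplicity. A reader could therefore suspect that the 90% is lost once the correction is applied, or could take 90% for 25 points as a promise for each of the three tests.

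If so, the primary comparisons might miss a benefit the investigators consider clinically significant, and a non-significant lidocaine-esmolol result might be read as equivalence. In addition, the placebo rate behind the calculation rests on 0 of 5 patients.

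**Working it through.** **Inputs.** From the Analytical Plan: difference 25 points, power 90%, confidence 95%, final size 50 per arm, pilot pain-free rates 0% (placebo), 40% (lidocaine), 60% (esmolol). Two inputs are inferred: the 0% placebo rate as the calculator entry, and a Bonferroni divisor of 3 from the comparison of all three groups.

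**Reproducing 32.** Unpooled formula: n = (z₁₋α/₂ + z₀.₉₀)² × [p₁(1−p₁) + p₂(1−p₂)] / d².

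- 0% against 25%, α = 0.05: (1.960 + 1.282)² × (0 + 0.1875) / 0.0625 = 10.51 × 3 = 31.5, so 32 per group.
- The same formula gives 43.3 (44) for 5% against 30% and 53.4 (54) for 10% against 35%, so for a 25-point difference only a placebo rate near 0% fits.
- 0% against 40% gives 10.51 × 0.24 / 0.16 = 15.8, or 16 per arm and 32 in total. That is not the stated 25-point difference, and the plan raises 32 to 50 per group, so 32 is read as per group.

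**Size needed at 0.05/3 = 0.0167.** The critical z becomes 2.394: (2.394 + 1.282)² × 3 = 40.5, so 41 per arm. The pooled-variance version gives 45. Both are below 50.

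**Power for 0% against 25% at 0.0167.** With no pain-free placebo patients and x pain-free patients on drug, Pearson's statistic with n per arm reduces to 2n·x / (2n − x). It must exceed 2.394² = 5.73.

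- n = 50: x = 5 gives 500/95 = 5.26, x = 6 gives 600/94 = 6.38. The test rejects at x ≥ 6, and P(Binomial(50, 0.25) ≥ 6) = 99.3%.
- n = 32: x = 5 gives 320/59 = 5.42, x = 6 gives 384/58 = 6.62. Again x ≥ 6, now with probability 84.7%. This shortfall belongs to a size the trial does not use.
- Normal approximation, n = 50: (0.25√50 − 2.394 × √(2 × 0.125 × 0.875)) / √0.1875 = (1.768 − 1.120) / 0.433 = 1.50, power 93.3%.
- Both drugs beating a placebo arm at 0%: 0.993² = 98.6%.
- A more conservative test does not change the answer: 98.1% with Fisher's exact test and 95.5% with a continuity correction.
- With a divisor of 2 (α = 0.025): 99.8% exact, 95.2% approximate.

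**Other scenarios, 50 per arm, α = 0.0167.** Placebo rates above 0% are assumptions. The exact 95% interval for 0 of 5 is 0 to 1 − 0.025^(1/5) = 52%.

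| Comparison | Exact | Approximate |
|---|---|---|
| 5% v 30% | 87.3% | 82.9% |
| 10% v 35% | 76.4% | 73.5% |
| 20% v 45% | 61.9% | 61.2% |
| 5% v 40% (lidocaine at its pilot rate) | 98.8% | 97.6% |
| 10% v 40% (lidocaine at its pilot rate) | 89.2% | 87.3% |
| 20% v 60% (esmolol at its pilot rate) | 97.0% | 96.8% |
| Lidocaine v esmolol, 40% v 65% | 58.5% | 54.5% |
| Lidocaine v esmolol, 60% v 85% | 67.8% | 66.4% |
| Lidocaine v esmolol, pilot gap 40% v 60% | 38.2% | 34.4% |

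**If the drug arms repeated the pilot rates** (20/50 against 30/50 pain-free): chi-square = 100 × (20×20 − 30×30)² / 50⁴ = 4.00, p = 0.046, which is not significant at 0.0167. The 98.3% interval for lidocaine minus esmolol is −0.20 ± 2.394 × √(0.24/50 + 0.24/50), or −43.5 to +3.5 points.

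**The case for a change.** The strongest case for a change has three parts.

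First, lidocaine against esmolol is a planned, corrected test, and 50 per arm gives it well under 90% power for 25 points at any of the rates tried. That is true, and a null result there would not show that the drugs are equivalent: the interval above still contains a 25-point difference. But the plan makes no power claim for this pair, and the 25-point figure is introduced after pilot results described relative to placebo. No commitment is broken, and the limitation would show in any ordinary report of the result.

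Second, the divisor is not written down, and a p-value between 0.0167 and 0.025 would change verdict with it. That could happen in principle. However, a comparison of all three groups, pair by pair, is three comparisons, so an analyst following the text divides by 3. A divisor of 2 would normally mean that the drug-to-drug test is outside the family, which sits badly with the plan's wording.

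Third, the placebo rate is poorly known, and power for a gain of exactly 25 points drops as it rises. This stands as a caution about a five-patient pilot. It is a separate matter from the correction, and it combines assumed placebo rates with a gain smaller than either pilot effect (40 and 60 points). At the pilot drug rates tabulated above, power stays at about 89% or higher.

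**Conclusion.** The mismatch is real but has no consequence for the primary tests under the plan's own assumption. Bonferroni raises the requirement from 32 to 41 per arm (45 with pooled variance), and 50 per arm more than covers it: 99.3% exact and 93.3% approximate, against a stated 90%. What is unstated (the divisor, power at 50, the limited power for lidocaine against esmolol) is detail that an analyst following the plan would supply sensibly. Stating it would change no sample size, test or endpoint.

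This rests on two inferences, a 0% placebo pain-free rate and a divisor of 3. The conclusion also holds with a divisor of 2. It does not extend to a gain of only 25 points over a placebo rate of 5% or more, where corrected power is 87% or lower by exact enumeration, nor to the comparison between the two drugs.

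### Optional gain: Shaffer's step-down keeps every Bonferroni rejection and raises lidocaine-versus-esmolol power from 38% to 54% at the pilot rates

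*Combined protocol and SAP*

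**What the plan says.** The Analytical Plan states the comparison in one sentence: "We will perform an individual comparison of all three groups using" Pearson's "chi-square test with Bonferroni correction for multiple comparisons". It gives neither the number of tests nor the adjusted level. Three groups make three pairs, so I read the level as 0.05/3 = 0.0167 per pair.

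The Objectives section is about each drug against placebo: "Our primary hypothesis is that esmolol and lidocaine, when given without the use of a tourniquet, provide relief of propofol injection pain" better than placebo does. Lidocaine versus esmolol is not named there. It is one of the three planned comparisons, and the Background gives a reason for interest in it, saying that esmolol "may be even more effective than lidocaine at attenuating propofol injection pain when used in combination with a tourniquet".

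The size calculation used a "25% difference considered clinically significant, 90% power, and a 95% confidence level to determine a sample size of 32" per group, then raised this to 50. The Sample Size section confirms that "150 patients (50 in each arm) is anticipated to be needed in this study". The pilot had five patients per arm. The no-pain rates were 40% on lidocaine and 60% on esmolol, "while 0% of patients who received placebo reported no pain"; Table 2 in the Appendix agrees.

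**The concern.** Bonferroni tests each pair as though all three null hypotheses could still be true, whatever the other results show. With three groups that is stricter than necessary. If one equality is false, the other two cannot both be true, because together they would imply the first. Once one pair has been declared different, there is at most one true null left to protect, and it can be tested at the full 0.05.

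The loss falls mainly on lidocaine versus esmolol, where the pilot difference is smallest. If the pilot rates recurred exactly in the main trial (20 of 50 against 30 of 50 without pain), that pair would be non-significant under the planned rule and significant under the step-down.

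**Working it through.** **Inputs.** 50 per arm (Sample Size). Pearson chi-square for three pairs with Bonferroni, 95% confidence, a 25-point design difference, and pilot no-pain rates of 0/40/60% for placebo/lidocaine/esmolol (Analytical Plan; Table 2). Three readings are mine: a divisor of 3, two-sided testing, and no continuity correction. The plan states none of them.

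**The plan's own figure.** The unpooled two-proportion formula at 0% versus 25%, two-sided 0.05 and 90% power gives

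n = (1.960 + 1.282)² × [0 × 1 + 0.25 × 0.75] / 0.25² = 31.5, rounded up to 32.

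The stated 32 is reproduced. It was calculated at the unadjusted level.

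**Error control.** Shaffer's rule compares the smallest p-value with 0.05/3 and, if that is significant, each of the others with 0.05.
- All three nulls true: any rejection needs the smallest p ≤ 0.05/3, so the chance is at most 3 × 0.05/3 = 0.05.
- Exactly one null true: rejecting it needs its own p ≤ 0.05.
- Exactly two nulls true: impossible.

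Nominal family-wise error is therefore 5% throughout, and no threshold is stricter than Bonferroni's.

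**Exact pilot pattern.** For 20/50 versus 30/50 the pooled rate is 0.5, so chi-square = 0.2² / (0.5 × 0.5 × 2/50) = 0.04/0.01 = 4.00 and p = 0.0455. This lies above 0.0167 and below 0.05. Against 20/50, Bonferroni first rejects at 32/50 (p = 0.0163).

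**Power.** I enumerated all 51³ outcomes of three independent binomial arms of 50. *Superior* means significant and in the favourable direction. Shaffer lost 0 Bonferroni rejections.

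| No-pain rates, placebo/lidocaine/esmolol | Question | Bonferroni | Shaffer |
|---|---|---|---|
| 0/40/60% (pilot) | lidocaine vs esmolol | 38.2% | 54.3% |
| 0/40/60% (pilot) | both drugs superior | 100% | 100% |
| 0/25/25% (design effect) | both drugs superior | 98.6% | 99.9% |
| 5/30/30% (assumed) | both drugs superior | 78.7% | 89.7% |
| 10/35/35% (assumed) | both drugs superior | 63.8% | 77.6% |
| 20/45/45% (assumed) | both drugs superior | 45.9% | 61.9% |
| 0/20/20% (assumed) | both drugs superior | 90.6% | 98.7% |
| 0/15/15% (assumed) | both drugs superior | 60.9% | 88.0% |

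The assumed rows are not in the documents. They show what happens if some placebo patients are pain-free or the effects are below 25 points. The pilot cannot exclude pain-free placebo patients: for 0 of 5 the exact 95% upper limit is 1 − 0.025^(1/5) = 52%.

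**Equivalent sample size.** For 40% versus 60%, Bonferroni power first reaches 54.3% at 76 per arm and stays above it from 81. The path is uneven because counts are discrete.

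**Price.** At 0/25/25%, false rejection of the truly equal pair rises from 1.7% to 5.1%. Its maximum over the common rate rises from 2.1% to 5.7%, both at 50%. The excess over 5% comes from the chi-square approximation at this sample size, not from the step-down. When all three arms are equal, the chance of any rejection is identical for both rules.

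**The case against.** The strongest reply is that nothing is broken, and that the headline gain concerns a pair to which the plan attaches no hypothesis, effect size or power. That is correct. For the stated hypothesis, the gain on the plan's own inputs is nil at the pilot rates and 99.9 − 98.6 = 1.3 points at the design effect.

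Other points also stand:
- **Size of the difference.** The pilot gap between the drugs is 60 − 40 = 20 points, below the 25 points that the plan calls clinically significant. Power of 54% is still low.
- **Thin pilot.** The two drug rates differ by one patient in five, and the plan's own intervals are 0–83% and 17–100%. With placebo at 0% and lidocaine at 40%, the change is 9.4% to 18.4% if esmolol is 50%, 21.0% to 34.5% at 55%, and 77.1% to 87.6% at 70%.
- **Choice of test.** With a continuity correction the headline becomes 31% to 46%, and p for 20/50 versus 30/50 is 0.072. The plan names Pearson's test without a correction, so the uncorrected figures are the fair reading.
- **Holm does as well here.** Holm's step-down also gives 54.3% at the pilot rates and 99.7% for both drugs at 0/25/25%. Shaffer pulls clearly ahead only under assumed rates, such as 77.6% against 68.6% at 10/35/35%.
- **False efficacy claims.** If one drug does nothing, its chance of being declared superior rises, for example from 0.9% to 2.5% at 20/45/20%.

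These points limit the weight of the suggestion. None makes the comparison of the two rules wrong: Shaffer never loses a Bonferroni rejection and has the same nominal family-wise error.

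**Conclusion.** The point holds as an optional efficiency gain. Bonferroni is valid and prespecified, and a team that prefers the simpler rule can reasonably keep it. At the pilot rates the step-down adds 54.3 − 38.2 = 16.1 points of power for lidocaine versus esmolol with no extra patients. For both drugs against placebo, the gain is material only if effects are below 25 points, or near 25 points with some placebo patients pain-free: 11 to 16 points at assumed placebo no-pain rates of 5–40% with equal 25-point effects. With pilot-size effects it is at most 2.2 points over assumed placebo rates up to 30%.

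The conclusion rests on three tests at a two-sided 0.05, the uncorrected Pearson test, 50 analysed patients per arm, and, for the headline, pilot rates from five patients per arm.

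**What to change.** If the data are still blinded, replace the Bonferroni clause with:

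> The three pairwise chi-square p-values will be tested by Shaffer's step-down procedure: the smallest is compared with 0.05/3; if it is significant, each of the other two is compared with 0.05.

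If the data are already unblinded, keep Bonferroni and write that there are three tests at 0.0167 each. If intervals are reported, give 98.3% intervals and say that they need not agree with the step-down decision.

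The cost is one sentence and the higher false-rejection rate for a single truly equal pair. Shaffer also has no simple matching simultaneous intervals, although the plan specifies none. The change does not replace a larger sample: at assumed placebo no-pain rates of 20–40% with 25-point effects, power for both drugs stays at 57–62%.
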